3.3 Preoperative bone health status prior to arthroplasty (See Bernatz, et. al. #1)⁴⁰

We hypothesized that preoperative osteoporosis is under-recognized and undertreated in the total joint arthroplasty (TJA) population. The purpose of this study was to determine preoperative osteoporosis prevalence prior to TJA and rates of pharmacologic osteoporosis treatment in the TJA population.

This was a retrospective case series of 200 consecutive adults (106F, 94M) age 48-92 years who underwent elective TJA (100 TKA, 100 THA) at the University of Wisconsin. Charts were reviewed to determine preoperative osteoporosis risk factors, prior osteoporosis screening and previous osteoporosis pharmacotherapy. Fracture risk was estimated using FRAX and NOF criteria for screening and treatment were applied to all patients.

119 of these 200 patients (59.5%) met criteria for osteoporosis screening, but only 21 (17.6 percent) had DXA performed in the two years prior to surgery. Forty-nine patients (24.5%) met NOF criteria for pharmacologic treatment but only 11 of these 49 received a prescription for pharmacotherapy within six months of surgery. Given that an estimated 1 million TKAs will be performed annually by 2020, if these results are generalizable it is likely that ~250,000 TKA patients are candidates for pharmacologic treatment. Thus, the majority of patients undergoing elective TJA met criteria for osteoporosis screening, however only a small percentage were. One quarter of these patients met criteria to receive pharmacotherapy but few are prescribed treatment. This lack of preoperative osteoporosis screening and treatment likely contributes to periprosthetic fracture risk.

3.4 Osteoporosis prevalence in well-functioning TKA patients 2-5 years after surgery (See Bernatz, et. al., #2)⁴¹

This study reports osteoporosis prevalence in a healthy cohort of patients with well-functioning TKA. We hypothesize that osteoporosis is under-recognized in this population.

This was a cross-sectional study of 30 adults (15 M/15 F) age 59-80 years selected to have no known bone health issues. Routine clinical DXA and custom distal femur scans were performed 2-5 years (mean 3.2 ± 0.8) after primary unilateral TKA. DXA examination included lumbar spine, hip and radius BMD, trabecular bone score and vertebral fracture assessment. These data, plus, clinical risk factors, were used to estimate fracture risk via FRAX and the WHO skeletal status classification (normal, osteopenic, osteoporotic) was determined. The NOF criteria for treatment were applied.

Six of these 30 patients (20%) had osteoporosis (lowest BMD T-score ≤ -2.5), 18 (60%) were osteopenic and 20% had normal BMD. Five patients with normal or osteopenic BMD had occult vertebral fractures on vertebral fracture assessment (VFA). Based on NOF guidelines, eleven (37%) patients met criteria for pharmacologic treatment.

The prevalence of unappreciated osteoporosis (37%) requiring treatment after TKA in this series of patients who were specifically excluded for known bone disease is substantial and may contribute to periprosthetic fracture risk. These data support the further study of postoperative osteoporosis and consideration of DXA testing after TKA.

4.0 STUDY DESIGN/METHODS

4.1 Patient cohort

Patients age ≥ 55 years and meeting entry criteria when the decision is made to proceed with TKA will be offered the option of study participation. Those consenting will receive a screening DXA (lumbar spine, bilateral femur/hip and VFA to determine eligibility. The inclusion/exclusion criteria (see below) are modeled after prior ABL clinical trials.

[figure not shown]
4.2 Participant recruitment and study design

Study participants will be recruited from the UW Total Joint Program at the American Center. Patients expressing interest in study participation at the time of TKA scheduling will subsequently be contacted by a University of Wisconsin Osteoporosis Clinical Research Program (OCRP) study coordinator. Those expressing study interest will be scheduled at the OCRP where, following informed consent, medical history, collection of FRAX risk factors and a screening DXA of the lumbar spine, bilateral femurs/hips and VFA will be performed.

The overall study design is noted in Figure 1. Briefly, study eligibility will be determined by DXA. Those with osteoporosis who elect ABL will make up the treatment group ($n = 29$). An equal number ($n = 29$) will be recruited into the untreated group, i.e., those with osteopenia and no prior fragility fracture.

At screening, all participants will have a physical examination and blood collected for a metabolic panel, 25(OH)D and parathyroid hormone (PTH) measurement with additional sample to bank for potential future testing related to bone metabolism. Additionally, calcium and PRO questionnaires will be collected consisting of the KOOS JR, VR-12, and Forgotten Joint Survey. Subjects will be advised on how to achieve a daily calcium intake of 1,000-1,200 mg through food plus supplements, if needed, and up to 4000 IU of vitamin D₃ daily (as noted below; section 5.1). Subsequently, for those meeting all inclusion/exclusion criteria, ABL will be initiated in the treatment group approximately 3 months (depending on the surgery schedule) prior to their TKA and serum calcium will be assessed after one month of dosing. Subsequently, all subjects will have lumbar spine and bilateral femur DXA repeated within two weeks prior to TKA (± 7 days from the month -0.25 study visit) and again 6 and 15 months post TKA. At these same visits, PRO questionnaires will be administered and blood will be collected for serum banking.

Figure 1: Study Design Schematic

4.3 Inclusion Criteria

1. Post-menopausal women and men age ≥ 55 years and scheduled to undergo primary TKA at the University of Wisconsin Total Joint Program.
2. Osteoporosis, i.e., BMD T-score (using female reference data) ≤ -2.5 at the lumbar spine, femoral neck OR total hip or ≤ -1.1 with VFA confirmed vertebral fracture or history of low-trauma nonvertebral fracture in the past 5 years OR osteopenia, BMD T-score (using female reference data) -1.1 to -2.4 at the lumbar spine, femoral neck or total hip and no prior low-trauma fracture.
3. Serum calcium (albumin-corrected), serum creatinine and PTH values all within the normal range and $25(\text{OH})\text{D} > 10 \text{ ng/mL}$.
4. Willing to supplement with daily calcium and/or vitamin D_3 at protocol specified doses.
5. Able to provide written informed consent.

4.4 Exclusion Criteria

1. Unevaluable distal femur BMD due to hardware or other artifacts.
2. History of bone disorders (e.g., Paget's disease) other than osteoporosis.
3. History of prior external beam or implant radiation therapy involving the skeleton other than radioiodine.
4. History of chronic or recurrent renal, hepatic, pulmonary, allergic, cardiovascular, gastrointestinal, endocrine, central nervous system, hematologic or metabolic diseases, or immunologic, emotional and/or psychiatric disturbances that, in opinion of the principal investigator, would compromise study data validity.
5. History of Cushing's disease, growth hormone deficiency or excess, hyperthyroidism, hypo- or hyperparathyroidism or malabsorptive syndromes within the past year.
6. History of significantly impaired renal function (serum creatinine $> 2.0 \text{ mg/dL}$. If the serum creatinine is > 1.5 and $\leq 2.0 \text{ mg/dL}$, the calculated creatinine clearance (Cockcroft-Gault) must be $\geq 37 \text{ mL/min}$).
7. History of nephrolithiasis or urolithiasis within the past five years.
8. History of cancer in prior 5 years (basal cell or squamous skin cancer is permissible).
9. History of osteosarcoma at any time.
10. Patients known to be positive for Hepatitis B, Hepatitis C, HIV-1 or HIV-2.
11. Known hypersensitivity to any of the test materials or related compounds.
12. Prior treatment with PTH- or PTHrP-derived drugs, (ABL, teriparatide or PTH (1-84)).
13. Prior treatment with IV bisphosphonates at any time or oral bisphosphonates within the past three years. Patients who had received a short course of oral bisphosphonate therapy (3 months or less) may be enrolled as long as the treatment occurred 6 or more months prior to enrollment.
14. Treatment with fluoride or strontium in the past five years or prior treatment with bone-acting investigational agents at any time.
15. Treatment with calcitonin the past 6 months or denosumab in the past 18 months.
16. Treatment with anticonvulsants affecting vitamin D metabolism (phenobarbital, phenytoin, carbamazepine or primidone) or chronic heparin within the prior 6 months.
17. Treatment with anabolic steroids or calcineurin inhibitors (cyclosporin, tacrolimus)
18. Daily treatment with oral, intranasal or inhaled glucocorticoids in the prior 12 months.
19. Exposure to any investigational drug within 12 months.
20. Consumption of > 2 alcoholic drinks per day or use of illegal drugs within 12 months of screening.
21. Not suitable for study participation due to other reasons at the investigators discretion.

5.0 VISIT SUMMARIES

Table 1: Assessment/Procedure Schedule

	Screen	Treatment Initiation ^{5,6}	Treatment Follow-up ⁶	Pre-Surgery	Visit 1 Follow-up	Visit 2 Follow-up
Time	Month -3.5	Month -3	Month -2	Month -0.25	Month 6	Month 15
Window			± 5 days	± 7 days	± 7 days	± 7 days
Informed Consent	X					
Medical History	X					
Confirm Eligibility	X ¹					
Vitals	X ²					
DXA ³	X			X	X	X
VFA	X	X ⁷	X ⁷	X ⁷	X ⁷	X ⁷
Body Composition ⁴	X			X	X	X
Physical Exam	X	X ⁷	X ⁷	X ⁷	X ⁷	X ⁷
Clinical Falls/Fracture Assessment		X	X	X	X	X
Comprehensive Metabolic Panel	X					
Parathyroid Hormone	X					
Total 25(OH)D	X					
Blood collection	X			X	X	X
Serum Calcium			X			
PRO & Diet questionnaires ⁸	X			X	X	X
ABL Administration Training	X ⁵	X				
Dispense calcium/vitamin D ⁹	X			X	X	
Dispense abaloparatide ¹⁰		X		X	X	

¹To be completed after laboratory results are available.

²To include blood pressure, pulse, height and weight

³To include lumbar spine, femur (hip and distal), forearm (PA & lateral knee performed on eligible subjects)

⁴To include total body DXA scan and Bioimpedance spectroscopy

⁵This can be an in-person, video or phone visit per subject preference

⁶Activity only completed by subjects taking abaloparatide

⁷Symptom driven evaluation, performed as appropriate

⁸Questionnaires include KOOS JR, VR-12, and Forgotten Joint Survey; Diet only performed at screening; Forgotten Joint only performed after surgery

⁹Dispensed to all subjects as determined at screening and/or pre-surgery per protocol

¹⁰Dispensed only to subjects in the treatment arm, some subsequent dispensing will occur via UPS every 3 months

5.1 Screening

Interested subjects will provide written informed consent and self-reported medical history to confirm study eligibility. Those meeting eligibility criteria will have DXA scans (lumbar spine, bilateral femur/hip, forearm and VFA) performed. Those with normal bone density based on a female normative database (i.e., T-scores ≥ 1.0) at the femoral neck, total proximal femur and lumbar spine (with vertebral exclusion per ISCD recommendations), will be excluded from further participation. Remaining potential subjects will receive PA and lateral knee DXA, body composition measurement by DXA and BIS, a physical exam with vitals (blood pressure, pulse, height and weight), complete a dietary calcium assessment and PRO questionnaires to include KOOS JR, VR-12 and Forgotten Joint Survey. Additionally, they will have blood collected to measure a comprehensive metabolic panel, PTH and total 25(OH)D. Samples will

also be collected for potential future testing related to bone metabolism related to this protocol. Those with abnormal calcium, creatinine, albumin, PTH or 25(OH)D < 10 ng/mL will be excluded from the study. DXA results performed within the prior 6 months on the research scanner are acceptable for the screening visit. Laboratory values and PRO questionnaires collected as part of a UWHealth evaluation in the 6 months prior to the screening visit can be utilized as screening data. Additionally, physical exam may be delayed to the initiation visit for the treatment group or pre-surgery visit for osteopenic group.

Subjects meeting the entry criteria based on osteoporosis diagnosis (T-score \leq -2.5 or -1.1 with prevalent vertebral fracture or recent low trauma clinical fracture) will discuss ABL treatment and those electing to participate will receive training on how to administer the medicine using the Radius ABL Instructions for Use (IFU) manual. Subjects declining treatment will be excluded from the study. Subjects in the osteopenia group will have a lowest BMD T-score of -1.1 to -2.4 at the lumbar spine, femoral neck or total proximal femur and a negative fragility fracture history.

All subjects meeting screening criteria will receive recommendations regarding daily calcium and vitamin D₃ optimization/supplementation during the study. Participants consuming less than 1000-1200 mg of calcium daily will be advised to take a supplement. If serum 25(OH)D is \geq 30 ng/mL no change in vitamin D supplementation will be initiated. For those whose 25(OH)D is 10.1-20.0 ng/mL, 4000 IU of daily vitamin D₃ will be provided, those between 20.1-30.0 ng/mL will receive 2000 IU daily. Supplementation will be provided as needed up to 500 mg of calcium and 4000 IU D₃.

5.2 ABL initiation

After screening labs have been reviewed and eligibility is confirmed, subjects in the treatment group will start daily ABL. As noted above, this will be initiated 12 weeks before scheduled TKA. If ABL is started greater than 12 weeks after screening, all DXA scans should be repeated at the treatment initiation visit. ABL will be administered daily for 18 months via self subcutaneous injection of 80 mcg. Each pen may be used for 30 days, as most pen volume exceeds this need, pens will be labeled with a start date. Research staff will call subjects each month and remind them to change out pens. A 3-month supply of ABL, vitamin D and calcium if needed, will be dispensed to subjects via mail or in person. For those having preparation mailed, the study coordinator will call to confirm package receipt, review dosing instructions and discuss adverse events. Those preferring live interaction will be offered video (e.g., facetime) or in person visits to pick-up supplies, review ABL dosing and meet with the study coordinator. A blood collection visit to measure serum calcium will be scheduled 4 weeks \pm 5 days after initiating ABL.

5.3 Treatment Follow-up

Only subjects in the treatment group will return to the OCRP for total calcium measurement. For any pre-dose serum calcium value that is >10.5 mg/dL, the hypercalcemia will be confirmed by prompt retesting. If a participants' pre-dose serum calcium is >10.5 mg/dL on repeat testing, calcium and vitamin D supplementation will be withheld and the serum calcium repeated 1-2 weeks later. If serum calcium is \leq 10.5 mg/dL, supplementation will not be restarted and ABL treatment continued. If hypercalcemia (> 10.5 mg/dL) persists the ABL dose will be reduced to 40 mcg. In this situation, a fasting serum calcium will be repeated in 1-2 weeks. If hypercalcemia (>10.5 mg/dL) persists despite dose reduction treatment will be discontinued and study participation terminated. Finally, subjects will be questioned regarding adverse events, falls and fractures; a physical exam or VFA may be performed if indicated per an investigator.

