5.4 Pre-TKA Study Visit

All subjects will have TKA surgery approximately 3 months after their screening DXA visit, depending on the surgery schedule. The osteopenic group must have screening data at least 4 weeks prior to but not more than 6 months before this visit. The osteoporotic group must have received at least 8 weeks of ABL prior to this visit. Such variability is acceptable as this reflects clinical care and the primary comparison is BMD change from immediately prior to surgery to 15 months after TKA. As the usual wait time for surgery scheduling in our facility is ~2 months, this should not present a major impediment to study recruitment. The week prior to their scheduled TKA surgery all subjects will return to the OCRP and have repeat lumbar spine, bilateral femur/hip (including distal femur), forearm, PA & bilateral knee and total body DXA measurement, BIS, blood collection and adverse event assessment. Calcium and vitamin D₃ will be dispensed as appropriate. Additionally, subjects will be questioned regarding adverse events, falls and fractures; a physical exam or VFA may be performed if indicated per an investigator. If surgery is delayed for any reason, the study physician will determine if study continuation is appropriate and adjust the study visit timeline as necessary, this may include repeating laboratory tests and/or DXA exams.

5.5 6-month

All subjects will return to the OCRP for DXA (lumbar spine, bilateral femur/hip (including distal femur), forearm, total body, PA & lateral knee), BIS measurement and blood collection. Subjects will be questioned regarding adverse events, falls and fractures and PRO questionnaires will be completed; a physical exam or VFA may be performed if indicated per an investigator. Calcium and vitamin D will be dispensed as needed.

5.6. 15-month

All subjects will return to the OCRP for DXA (lumbar spine, bilateral femur/hip (including distal femur), forearm, PA & lateral knee and total body), BIS measurement and blood collection. Subjects will be questioned regarding adverse events, falls and fractures and PRO questionnaires will be completed; a physical exam or VFA may be performed if indicated per an investigator.

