6.4 Laboratory

A comprehensive metabolic panel, calcium and PTH will be measured at the UW Clinical Laboratories per their standard clinical approach. Vitamin D research best practices require 25(OH)D measurements be performed using chromatography-based methodologies, consequently, 25(OH)D will be measured in the clinical laboratory using high performance liquid chromatography (HPLC).

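### After hypercalcemia is confirmed and then corrected under section 5.3, ABL continues for about 16 to 17 months with no further scheduled serum calcium; one test at the existing Month 6 draw would be a cheap safeguard

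*Combined protocol and SAP*

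**What the plan says.** Section 5.2 sets the course: "ABL will be administered daily for 18 months via self subcutaneous injection of 80 mcg". Section 4.2 plans one safety calcium: "serum calcium will be assessed after one month of dosing". Section 5.2 places it at 4 weeks, give or take 5 days. Table 1 agrees: the serum calcium row is marked only at Month -2, and the metabolic panel only at screening.

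Section 5.3 says what follows a high value:

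- A pre-dose calcium above 10.5 mg/dL is retested promptly. No number of days is given.
- If confirmed, "calcium and vitamin D supplementation will be withheld and the serum calcium repeated 1-2 weeks later".
- If that repeat is at or below 10.5 mg/dL, "supplementation will not be restarted and ABL treatment continued".
- If it is still high, the dose falls to 40 mcg. "In this situation, a fasting serum calcium will be repeated in 1-2 weeks". If calcium remains high, ABL is stopped and participation ends. The text does not say what happens after a normal value at 40 mcg; continuation is implied.

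Sections 5.4 to 5.6 name no calcium assay at the pre-TKA, Month 6 or Month 15 visits. Blood is drawn at all three, but section 4.2 gives its purpose: "PRO questionnaires will be administered and blood will be collected for serum banking". Section 6.4 names the laboratory ("A comprehensive metabolic panel, calcium and PTH will be measured at the UW Clinical Laboratories per their standard clinical approach") and adds no time points.

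**The concern.** Section 5.3 treats calcium above 10.5 mg/dL as serious enough to withhold supplements, then halve the dose, then stop the drug, and section 5.9 makes the last step mandatory. Those rules can act only on a measured value. For the subjects who have already shown confirmed hypercalcemia on ABL, the last planned value is one normal result 1 to 2 weeks after a change in management. It falls before surgery on the nominal 12-week lead-in, so on that schedule no planned calcium covers the whole post-operative part of treatment.

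The corrective step may also be weak for some subjects. Sections 5.1 and 6.2 provide supplements only as needed. For a subject taking none, withholding them changes nothing, and ABL continues at full dose after one normal value.

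What is at stake is a silent recurrence during long further dosing. Monthly calls and adverse-event questions can pick up symptoms but do not measure calcium.

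**Working it through.** **Plan's own duration.** Month -3 to Month 15 is 3 + 15 = 18 months, as section 5.2 states. At 30.44 days per month, 18 × 30.44 = 547.9 days.

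**Day of the last planned calcium, counted from the first dose.**

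- Week-4 draw: 28 ± 5, so day 23 to 33 (section 5.2).
- Prompt retest: assumed 1 to 7 days later, so day 24 to 40.
- Repeat off supplements, 7 to 14 days later (section 5.3): day 31 to 54.
- Fasting repeat on 40 mcg, a further 7 to 14 days later (section 5.3): day 38 to 68.

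**Treatment remaining = 547.9 − day of last planned calcium.**

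| Branch | Days | Months |
|---|---|---|
| 80 mcg, supplements off | 547.9 − 54 = 494 to 547.9 − 31 = 517 | 16.2 to 17.0 |
| 40 mcg (continuation implied) | 547.9 − 68 = 480 to 547.9 − 38 = 510 | 15.8 to 16.8 |

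Sensitivity: if the retest takes 14 days, the low ends become 16.0 and 15.5 months. If ABL ends at the Month 15 visit after a 12-week lead-in, the course is 17.8 months, and the 80 mcg low end with a 7-day retest is 16.0 months. After the shortest lead-in it is 15.3 months.

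**Effect of one calcium at Month 6.** With TKA at day 84 (12 weeks), Month 6 is day 84 + 182.6 = 266.6.

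- Before it, 80 mcg: 266.6 − 54 = 213 to 266.6 − 31 = 236 days.
- Before it, 40 mcg: 266.6 − 68 = 199 to 266.6 − 38 = 229 days.
- After it: 547.9 − 266.6 = 281 days, or 274 to 288 with the ±7-day visit window.

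Section 5.4 allows a shorter lead-in: "The osteoporotic group must have received at least 8 weeks of ABL prior to this visit". With the pre-TKA visit at day 56 and TKA assumed at day 63, Month 6 is day 63 + 182.6 = 245.6. Then 547.9 − 245.6 = 302 days follow, or 295 to 309 with the window.

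The interval after Month 6 is the longer part throughout. The cut in the longest untested interval runs from 1 − 309/480 = 36% (40 mcg, shortest lead-in, early visit) to 1 − 274/517 = 47% (80 mcg, 12-week lead-in, late visit). The untested time left after Month 6 is 274/30.44 = 9.0 to 309/30.44 = 10.2 months.

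**How many subjects.** The documents give no rate, so a range is assumed for confirmed hypercalcemia among the 29 treated.

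| Assumed rate p | 29 × p | 1 − (1 − p)^29 |
|---|---|---|
| 1% | 0.3 | 25% |
| 3% | 0.9 | 59% |
| 5% | 1.5 | 77% |
| 10% | 2.9 | 95% |

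These are upper bounds for subjects who reach the gap, because those still high on 40 mcg are stopped. They say nothing about how often calcium rises again.

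**The case against.** The strongest reply is that 5.3 does not wave a hypercalcemic subject through. The normal value follows withdrawal of calcium and vitamin D, which then stay off, and in the other branch the dose is also halved. Entry requires normal calcium, creatinine and PTH. Recent parathyroid disorders or malabsorption, significant renal impairment and recent stones are excluded. Staff call monthly, adverse events are asked about at visits, and laboratory tests may be repeated if surgery is delayed. The 5.3 steps apply to any pre-dose value, so an unscheduled high result would trigger them. All of this stands and lowers the risk, but none of it schedules a calcium.

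A second reply is that the choice of Month 6 is pragmatic: nothing in the documents makes 16 untested months unacceptable and 9 acceptable. That also stands. Month 6 is proposed because a draw already takes place there in mid-treatment.

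A reader might infer more than the documents support:

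- That ABL is continued in subjects who are still hypercalcemic. It is not; persistent elevation leads to dose reduction and then to stopping.
- That every treated subject is under-monitored. A single test for those normal at week 4 is the sponsor's choice, and nothing here shows it to be wrong.
- That 5.9 conflicts with 5.3. It lists the outcome of the last 5.3 step.
- That recurrences would go unnoticed. The documents do not describe care outside the study, so this cannot be said.
- That a material number of subjects will be harmed. No rate of first occurrence or recurrence is given.

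**Conclusion.** The point holds as a minor safety improvement. Following the schedule exactly leaves subjects with confirmed and then corrected hypercalcemia without a planned calcium for about 16.2 to 17.0 months at 80 mcg with supplements off. On the implied 40 mcg branch it is about 15.8 to 16.8 months. The two ranges belong to different subjects and should not be merged.

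The figures assume a retest within 7 days and a full 18-month course. The count of at most 0.3 to 2.9 subjects rests on an assumed 1% to 10% rate; the number who continue ABL would be lower if any are stopped at 40 mcg. The primary endpoint, sample size and analysis method are unaffected.

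**What to change.** In Table 1, 5.3 and 5.5, add: Any subject with hypercalcemia confirmed under 5.3 who continues ABL will have a pre-dose serum calcium at the Month 6 blood draw, sent to the UW Clinical Laboratories, and will hold that day's injection until the draw. If the value is above 10.5 mg/dL on prompt retest, the next unused step applies. (a) On 80 mcg with supplements already withheld: reduce to 40 mcg, repeat a fasting calcium in 1-2 weeks, and discontinue if still above 10.5 mg/dL. (b) Already on 40 mcg: discontinue under 5.9.

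It would help to state in 5.3 that a normal fasting value at 40 mcg means ABL continues at that dose. A test at the Month -0.25 visit is optional and adds little: on the nominal schedule (day 77) it falls 77 − 68 = 9 to 77 − 31 = 46 days after the last 5.3 value.

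Cost: about 0 to 3 assays in total under the assumed range, at a draw that already exists, plus a retest and possibly one repeat for a subject with a high value. A confirmed recurrence could add a withdrawal; section 8.0 allows for 29 − 21 = 8 losses. The 9 to 10 months after Month 6 stay untested. Closing that gap would need a new draw and is not requested.
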